- Determine the window around a specific nominal Rx day by adding or subtracting half of the interval between adjacent visits (e.g., days between Week 4 and Week 8 is 28). The threshold between adjacent visits is determined by splitting the interval evenly between the visits. If the resulting split is between Rx days, then the threshold is determined as the midpoint between the adjacent visits. If the resulting split is on an Rx day, then the threshold is determined as being between that Rx day and the Rx day prior to it (e.g., the split between Week 4 and Week 8 would be between Rx Days 43 and 44).
- If more than one assessment is included in a time window the assessment closest to the nominal day will be used. If there are two observations equidistant to the nominal day, the later one will be used in analyses. If more than one assessment is included on the same day, then the worst assessment on that day will be used in analyses, except those specified in Section 11.0.

The following analysis windows have been specified for the analysis of efficacy, laboratory parameters, and vital signs, etc. for each analysis period. In order to include all post baseline data, the first post baseline interval starts on the day after the date of first study drug injection in each period (Rx Day 2) for all efficacy variables.

For subjects who were randomized and not dosed date of randomization will be used for determining window definitions.

Table 2.
Visit Windows for Analysis of PASI, Vital Signs, and Local Tolerability in Part A (ITT/PP/Safety Populations)

Window Label	Target Day	Interval
Baseline	1	$\leq 1^a$
Week 4	29	[2, 43]
Week 8	57	[44, 71]
Week 12	85	[72, 99]
Week 16	113	[100, 127 ^b]

Rx Day calculated relative to first dose date of study drug. For subjects randomized but not dosed, Rx Day calculated relative to Randomization.

- a. There is no baseline for local tolerability measurements. If time is collected in vital signs, restrict to records prior to the first dose of study drug.
- b. The minimum of upper bound and the day of the first dose date in Part B (and within 105 days of last dose for safety analyses).

Table 3.
Visit Windows for Analysis of Safety Laboratory Tests in Part A (Safety Population)

Window Label	Target Day	Interval
Baseline	1	≤ 1
Week 8	57	[2, 85]
Week 16	113	[86, 141*]

Rx Day calculated relative to first dose date of study drug.

* The minimum of upper bound, the day of the first dose date in Part B, and 105 days of last dose.

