Table 4.
Visit Windows for Analysis of ECG in Part A (Safety Population)

Window Label	Target Day	Interval
Baseline	1	≤ 1
Week 4	29	[2, 71]
Week 16	113	[72, 155*]

Rx Day calculated relative to first dose date of study drug.

* The minimum of upper bound, the first dose date in Part B, and the last dose + 105 days.

Table 5. Visit Windows for Analysis of sPGA, PSS, DLQI, HAQ-DI, Pain VAS, Investigator's Global Assessment VAS, Patient's Global Assessment VAS, CRP as an ACR 20 Component, SJC, and TJC in Part A (ITT Population)

Window Label	Target Day	Interval
Baseline	1	≤ 1
Week 16	113	[2, 225*]

Rx Day calculated relative to first dose date of study drug. For subjects randomized but not dosed, Rx Day calculated relative to Randomization.

* The minimum of upper bound and the day of the first dose date in Part B.

Table 6. Visit Windows for Analysis of PASI, Vital Signs, and Local Tolerability in Part B (ITT/Safety Population)

Window Label	Target Day	Interval
Entry of Part B	1	$\leq 1^a$
Week 22	43	[2, 64]
Week 28	85	[65, 106]
Week 34	127	[107, 148]
Week 40	169	[149, 190]
Week 46	211	[191, 232]
Week 52	253	[233, 267]
Week 56	281	[268, 295 ^b]

Rx Day calculated relative to the first dose date on or after Week 16 for PBO/RZB_75 and PBO/RZB_150 arms, and relative to the date of Week 16 visit for RZB_75/RZB_75 and RZB_150/RZB_150 arms. PASI only evaluated from Week 22 to 52. Local tolerability only evaluated from Week 22 to 40.

a. If time is collected for vital sign, restrict to records prior to the first dose of study drug in Part B.

b. The minimum of upper bound and 105 days after the last dose.

Subjects who enter the Open Label Extension Study 1311.31 will not have Week 56 evaluations.

Table 7. Visit Windows for Analysis of sPGA, PSS, DLQI, HAQ-DI, Pain VAS, Investigator's Global Assessment VAS, Patient's Global Assessment VAS, SJC, TJC, Laboratory Tests, and ECG in Part B (ITT/Safety Population)

Window Label	Target Day	Interval
Entry of Part B	1	≤ 1
Week 28	85	[2, 127]
Week 40	169	[128, 211]
Week 52	253	[212, 294 ^a]

Rx Day calculated relative to the first dose date on or after Week 16 for PBO/RZB_75 and PBO/RZB_150 arms, and relative to the date of Week 16 visit for RZB_75/RZB_75 and RZB_150/RZB_150 arms.

a. The minimum of upper bound and 105 days after the last dose.

Table 8. Visit Windows for Summary of Study Drug Injections in Part A

Window Label	Target Day	Time Window
Week 0	1	≤ 1
Week 4	29	[2, 57 ^a]

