10.1.4 Missing Data Imputations

Missing data will be imputed using the following methods for the efficacy analyses:

- Non-Responder Imputation (NRI): The NRI analysis will categorize any subject who has missing value at a specific visit as non-responder for that visit. The only exception is when if the subject is a responder both before and after this specific visit window, then the subject will be categorized as a responder for the visit. The NRI will be the primary approach in the analysis of categorical variables. Of note, this before- and after-window imputation will utilize visits across Part A and B for the risankizumab arms.
- Last Observation Carried Forward (LOCF): The LOCF analyses will use the completed evaluation from the previous visit for efficacy measures assessed to impute missing data at later visits. For observations in RZB_75/RZB_75, and RZB_150/RZB_150 arms in Part B, LOCF is continued across Part A and Part B. LOCF will be applied to the observations in PBO/RZB_75, and PBO/RZB_150 arms within the analysis period. Baseline values will not be carried forward. LOCF will be the primary approach in the analyses of continuous variables, and the secondary approach in the analyses of categorical variables.
- As-observed: The as-observed analysis will not impute values for missing evaluations, and thus a subject who does not have an evaluation on a scheduled visit will be excluded from the as observed analysis for that visit. As-observed analysis will be the secondary approach in the analysis of continuous variables.
- Multiple Imputation (MI): The MI will be used as sensitivity approach to impute missing data in primary endpoints. The variables to be included in the imputation model are listed below. If MI is not applicable due to the nature of our data (e.g., MCMC algorithm does not converge), logistic regression or mixed effect model repeat measurement (MMRM) methods will be applied as sensitivity approach, whichever applicable.

The Multiple Imputation analysis will be carried out in three steps.

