- Imputation of missing data. The imputation will be generated for each efficacy endpoint measurement. The variables to be included in the imputation model are: concomitant disease of Baseline disease severity (PASI and sPGA), Baseline weight, treatment group, Concomitant PsA at baseline (Yes: Diagnosed or Suspected; versus: No), and measurements at each visit from randomization up to the end of the analysis period. For each endpoint, 20 'complete' datasets will be generated using SAS PROC MI. The imputed post-baseline measurements will be rounded to the same precision as the observed data before the determination of responder status (e.g., PASI90).
- Analysis of imputed data sets. A CMH test, stratified by stratification factors, will be used to analyze categorical endpoints in each imputed dataset.
- Synthesis of imputation and analysis results. SAS PROC MIANALYZE will be used to generate the final inferences of the risk difference between treatment groups.

Of note, subjects who discontinued due to AE of "worsening of disease under study" will be counted as non-responders in all subsequent visits in the NRI and MI analyses, and will have their last observation prior to discontinuation carried forward in the LOCF analyses. For Observations in RZB_75/RZB_75, and RZB_150/RZB_150 arms in Part B, LOCF is continued across Part A and Part B. LOCF will not carry forward from Period A to Period B for PBO/RZB_75, and PBO/RZB_150 arms.

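### SAP Table 5 scores a pre-Week-16 leaver's EOT value as an observed Week 16 value, so NRI is bypassed for the binary sPGA, ACR 20, DLQI and PSS endpoints

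*SAP*

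**What the plan says.** **Windows (SAP 6.0, Definition of Analysis Windows).** To keep all post-baseline data, "the first post baseline interval starts on the day after the date of first study drug injection in each period (Rx Day 2". Table 5 covers sPGA, PSS, DLQI, HAQ-DI, the VAS scales, joint counts and CRP as an ACR 20 component. Its only post-baseline row in Part A is Week 16: target Day 113, Days 2 to 225. The footnote limits the upper end: "The minimum of upper bound and the day of the first dose date in Part B". Table 2, for PASI, has four rows, and its Week 16 row runs from Day 100 to Day 127 with the same cut.

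**Choice within a window (SAP 6.0).** "If more than one assessment is included in a time window the assessment closest to the nominal day will be used". No maximum distance from the nominal day is set.

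**Leavers (Protocol 6.2.3.1, Flow Chart, 10.3.2).** A patient who will not continue completes the EOT procedures in place of the planned visit, and returns for FU3 16 weeks after the last dose. EOT includes sPGA, PASI, the patient-reported outcomes and, for eligible PsA patients, the joint and VAS assessments. None of these is scheduled at FU3.

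**Missing data (SAP 10.1.4).** "The NRI analysis will categorize any subject who has missing value at a specific visit as non-responder for that visit". The one stated exception is a patient who responds both before and after the visit, and "this before- and after-window imputation will utilize visits across Part A and B for the risankizumab arms". NRI is the primary approach for categorical variables. "LOCF will be the primary approach in the analyses of continuous variables, and the secondary approach in the analyses of categorical variables". As-observed analysis is secondary for continuous variables. Leavers due to an AE of worsening of disease "will be counted as non-responders in all subsequent visits in the NRI and MI analyses". SAP 10.3 gives the binary Week 16 secondary endpoints the same methods as the primary endpoint.

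**The concern.** NRI acts only when the Week 16 value is missing. For the Table 5 measures, a patient who leaves at Week 4, 8 or 12 and attends EOT has a value that the window calls Week 16, so nothing is missing and nothing is imputed. The plan names NRI as primary and LOCF as secondary, yet for these patients the two give the same result. The LOCF analysis therefore cannot reveal the difference it is there to test.

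The handling is also inconsistent within one patient and one visit: the PASI value leads to a Week 16 non-response, while the sPGA value counts as observed at Week 16. PASI 75 and sPGA 0/1 are both secondary endpoints compared with placebo at Week 16. What is at stake is the size and meaning of those secondary and further estimates.

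**Working it through.** **1. Reproduce the table bounds.**
- Table 2: half the Week 12 to Week 16 interval is (113 − 85)/2 = 14, and 113 + 14 = 127.
- Table 5: baseline to Week 16 is 113 − 1 = 112, and 113 + 112 = 225.
- Table 8 ("Visit Windows for Summary of Study Drug Injections in Part A") follows the same symmetric pattern: 29 + (29 − 1) = 57.

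**2. Follow a leaver through the windows.** EOT replaces the visit at Day 29, 57 or 85. The last dose was on Day 1 or Day 29, so FU3 falls on Day 1 + 112 = 113 or 29 + 112 = 141. FU3 brings no Table 5 measure and no PASI, so no later value displaces the one from EOT. There is no Part B dose, so the footnote cut never applies.

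| Day of value | PASI (Table 2) | sPGA etc. (Table 5) | PASI at Week 16 under NRI | sPGA at Week 16 under NRI |
|---|---|---|---|---|
| 29 | Week 4 | Week 16 | non-response | EOT result counts |
| 57 | Week 8 | Week 16 | non-response | EOT result counts |
| 85 | Week 12 | Week 16 | non-response | EOT result counts |
| 113 | Week 16 | Week 16 | observed | observed |

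The before-and-after exception cannot rescue PASI for an early leaver, because there is no later visit.

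**3. The late end of the window.** The Week 28 visit is Day 197 ± 7, that is Days 190 to 204, which lies inside Day 225. For a patient with no Part B dose and no Week 16 value, a Week 28 value would be labelled Week 16.

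**4. ACR 20.** CRP is also a safety laboratory test taken at Week 8, so the window can hold two values. For EOT on Day 85 the distances from Day 113 are 28 days (EOT) and 56 days (Day 57), so the EOT value is used and the result is the same.

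**5. Continuous endpoints.** Under LOCF an early EOT value would be carried to Week 16 in any case. Under the as-observed analysis the patient should drop out of Week 16, but Table 5 keeps the early value in.

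**6. Size.** Each arm has 56 patients in Part A (Protocol 7.7). One affected responder moves an sPGA arm rate by 1/56 = 1.8 points, two by 3.6 and three by 5.4. The illustration below assumes placebo at 3/56 and every affected responder in the active arm, which is the extreme case. It uses the unstratified difference d with z = d / √[p₁(1 − p₁)/56 + p₀(1 − p₀)/56]. The first column is the active count as Table 5 scores it.

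| Active count | 0 affected | 1 | 2 | 3 |
|---|---|---|---|---|
| 36/56: difference (z) | 58.9 (8.3) | 57.1 (8.0) | 55.4 (7.7) | 53.6 (7.4) |
| 48/56: difference (z) | 80.4 (14.5) | 78.6 (13.7) | 76.8 (12.9) | 75.0 (12.3) |

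With one affected responder in each arm the difference does not move: 35/56 − 2/56 = 33/56 = 58.9 points. The size of the ACR 20 subset is not given. If it were 5, 10 or 15 per arm (assumed), one patient would move that rate by 20, 10 or 6.7 points.

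**The case against.** The windows are pre-specified and the SAP gives a reason for the Day 2 start. PASI has narrower windows because it is measured at more visits, and the NRI rule itself is the same for both. Few patients can be affected: one must leave before Week 16, attend EOT, be a responder there, and not leave for an AE of worsening of disease. Patients who only stop drug are asked to stay for all visits. The secondary endpoints lie outside the multiplicity scheme.

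Most of this stands, and it limits the size. It does not remove the point. An early row keeps all post-baseline data just as well, without calling a Day 29 value Week 16, and the window still overrides the declared primary approach.

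Stronger readings that a reader might infer, and that the documents do not support:
- **Day 225 is an error.** Tables 2 to 4 add half the preceding interval, which here would give 113 + 56 = 169. But 225 is symmetric about Day 113 and Table 8 follows the same pattern, so it is a convention and not a breach.
- **The active arms are inflated.** Protocol 1.2 reports PASI 75 by Week 12 in 87% on active and none on placebo in the phase I trial. That is a single-dose study with a different measure and no Week 4 or Week 8 rate, and early leavers are a selected group. The net direction is not established.
- **The main result is at risk.** PASI uses Table 2, so PASI 90, PASI 75 and PASI 100 are untouched.

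**Conclusion.** The point holds as a conflict between the Table 5 window and the declared NRI approach. It affects binary sPGA 0/1 and ACR 20 at Week 16 (secondary) and sPGA 0, DLQI 0/1 and PSS 0 (further). It also reaches the as-observed Week 16 analysis of the continuous Table 5 endpoints and, for a patient with no Part B dose and no Week 16 value, can relabel a later value as Week 16.

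Not affected are the primary endpoint, the two hierarchical tests, patients with a real Week 16 value (the closest value is used), leavers due to an AE of worsening of disease, and leavers with no EOT assessment.

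The mechanism follows from the text alone. The size does not: the documents give no number of such leavers, no EOT response rate and no ACR 20 subset size. The effect is nil if there are no such leavers and is probably small otherwise. Significance is not expected to change; in the illustration z stays at 7.4 or above. The change should be made because the rule contradicts the stated method and is cheap to correct.

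**What to change.** In Table 5:
- Set Week 16 to match PASI in Table 2: Day 100 to the earlier of Day 127 and the first Part B dose date, for the NRI and as-observed analyses.
- Add an early post-baseline row, Days 2 to 99. Early EOT values are then kept, and are carried forward to Week 16 only in the LOCF analyses.
- Use the same Week 16 interval for the binary and continuous versions of each instrument, for example DLQI 0/1 and change in DLQI.

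Add a sentence to SAP 10.1.4 saying whether a response in the early row may serve as the earlier of the two responses in the before-and-after rule. For an early leaver this has no effect.

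The cost is one row, one changed interval and one sentence, with no new data. A few early leavers become non-responders under NRI or are excluded from the as-observed analysis at Week 16. A rare Week 16 visit after Day 127 counts as missing, as it already does for PASI. The planned visit window is Day 113 ± 3, so Day 127 leaves 127 − 116 = 11 further days.

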6.2.3.1 Early treatment and trial termination

If study medication is discontinued prior to the planned [Flow Chart](#) EOT visit, every effort should be made to have the patient continue in the trial and complete all of the remaining Treatment Period Visits, as well as Follow-Up 1 and Follow-Up 2 Visits. Trial termination should be completed at Follow-Up 2 Visit and Follow-Up 3 Visit should not be completed.

If a patient cannot or will not continue in the trial, the patient should complete EOT visit procedures instead of the planned treatment period visit and return to the clinic for Follow-Up 3/End of Observation (FU3/EOO) Visit 16 weeks after last dose of study medication.

Patients who discontinue treatment early should be registered as withdrawn/discontinued in IRT will not have the option to participate in the extension trial.

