5.0 Analysis Populations and Stratification

5.1 Analysis Populations

In this SAP, Part A refers to Week 0 to Week 16, and Part B refers to Week 16 and after.

Intent-to-Treat (ITT) Population: The ITT Population is defined as all subjects who are randomized at Week 0. ITT Population will be used for the efficacy analyses in Part A and Part B, as well as efficacy across the entire study (cross-period) for subjects who are randomized to risankizumab arms. Subjects who are randomized to placebo in Part A and do not continue into Part B will be excluded from the analysis in Part B.

ITT Population will be analyzed by treatment group as randomized.

Per-Protocol (PP) Population: To evaluate the impact of protocol deviations on the primary endpoint, additional efficacy analyses will be performed on a PP Population. The PP Population will include those who were most compliant with the protocol in ways that could impact the primary endpoints. Final results and the criteria for exclusion of subjects will be finalized prior to database lock.

The PP Population is defined as all subjects from the ITT Population who meet all the following criteria:

- Subjects must receive at least 75% of planned study drug injections (including dummy placebo injections) in Part A (prior to Week 16).
- Subjects must have at least one PASI assessment post-baseline.
- Inclusion Criterion 2: Subjects must have stable moderate to severe chronic plaque psoriasis at baseline:
 - Have an BSA $\geq 10\%$ and
 - Have a PASI ≥ 12 and
 - Have an sPGA ≥ 3 .

Final results and the criteria for exclusion of subjects will be finalized prior to the interim database lock.

PP Populations will be analyzed by treatment group as randomized.

Safety Population: Safety analyses will be performed on a Safety Population, comprising all randomized participants who received at least one dose of study drug in Part A. The safety analysis will be performed based on the actual treatment received at the randomization visit. Subjects who do not continue into Part B will be excluded from the Part B specific safety analysis. All safety analyses will be conducted on the Safety Population.

All Risankizumab Treated (ALL_RZB) Population: The ALL_RZB Population is defined as subjects who receive at least one dose of risankizumab in the study. Key safety summaries will be provided on the ALL_RZB Population.

Table 1. Notation for Treatment Groups

Population	Treatment Code	Definition

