ITT/Safety (Part A)	RZB_75	Subjects who randomized to risankizumab 75 mg.
	RZB_150	Subjects who randomized to risankizumab 150 mg.
	PBO	Subjects who randomized to either of the two placebo arms.
ITT/Safety (Part B)	RZB_75/RZB_75	Subjects who randomized to risankizumab 75 mg.
	RZB_150/RZB_150	Subjects who randomized to risankizumab 150 mg.
	PBO/RZB_75	Subjects who randomized to placebo and then risankizumab 75 mg entered Part B
	PBO/RZB_150	Subjects who randomized to placebo and then risankizumab 150 mg entered Part B
ITT/Safety (entire study)	RZB_75/RZB_75	Subjects who randomized to risankizumab 75 mg.
	RZB_150/RZB_150	Subjects who randomized to risankizumab 150 mg.
ALL_RZB	ALL_RZB	Subjects who received at least one dose of risankizumab 75/150 mg.

5.2**Variables Used for Stratification of Randomization**

Randomization will be stratified by concomitant PsA at baseline (Yes versus No) and body weight (≤ 90 kg versus > 90 kg).

6.0**Analysis Conventions****Definition of Baseline**

The last non-missing observation collected on or before the date of the first dose of study drug injection will be used as Baseline for summary of demographics and disease characteristics, safety and efficacy analyses, with the exception that:

- The last evaluation on or prior to the date of first dose of risankizumab will be used for the safety analyses in Part B among subjects randomized to placebo at Week 0, and the safety analyses in the ALL_RZB Population.
- For all vital sign assessments, only assessments prior to first dose time will be considered, since vital signs are to be assessed both pre- and post-dose in some visits.

Entry of Part B is defined as the last non-missing observation collected on or before the date of the first dose of study drug in Part B for PBO/RZB_75 and PBO/RZB_150 arms and last non-missing observation collected on or before the date of Week 16 visit for RZB_75/RZB_75 and RZB_150/RZB_150 arms.

Definition of Final Observation (Applicable to Safety Analyses)

Final observation in Part A is defined as the last non-missing observation collected within 105 days following the last dose of study drug in Part A for those who do not enter Part B, and on or before the first dose date of study drug injection in Part B for subjects who entered Part B. For vital sign assessments, only assessments prior to the first dose of study drug injection in Part B will be included in the analysis for Part A.

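### SAP Table 7 carries the 105-day safety cut-off into Week 52 ITT efficacy windows, so some early stoppers' observed Week 52 sPGA and ACR 20 data are dropped while their PASI is kept

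*SAP*

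**What the plan says.** **The cap.** SAP Section 6.0, Table 7 serves two purposes. Its title lists sPGA, PSS, DLQI, HAQ-DI and the VAS scales and ends with "SJC, TJC, Laboratory Tests, and ECG in Part B (ITT/Safety Population". The Week 52 row has target Day 253 and interval [212, 294], with the footnote "a. The minimum of upper bound and 105 days after the last dose". The Week 28 and Week 40 rows have no footnote.

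**PASI.** Table 6 gives PASI a Week 52 interval of [233, 267] with no footnote. The 105-day cap appears there only on the Week 56 row, and the table note says "PASI only evaluated from Week 22 to 52". The cap therefore never reaches PASI.

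**The same limit elsewhere in Section 6.0.**
- Table 2 (PASI with safety variables, Part A) adds the limit only in the form "and within 105 days of last dose for safety analyses".
- Table 5, the Part A counterpart of Table 7 for the efficacy variables, has no 105-day term: "The minimum of upper bound and the day of the first dose date in Part B".
- The last-observation rule that uses 105 days is headed "Definition of Final Observation (Applicable to Safety Analyses".

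**Population and follow-up.** SAP Section 5.1 says "ITT Population will be used for the efficacy analyses in Part A and Part B". For patients who stop drug early, protocol Section 6.2.3.1 says "every effort should be made to have the patient continue in the trial and complete all of the remaining Treatment Period Visits", and it extends this to the first two follow-up visits, the second of which is Week 52.

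**The concern.** The protocol asks patients who stop drug to keep attending so that they can be analysed as randomised. Read literally, footnote a then removes their Week 52 sPGA, joint, VAS, HAQ-DI, PSS and DLQI data because too much time has passed since the last dose. That is an on-treatment rule inside an ITT efficacy analysis, and it applies to some endpoints and not to others. For one patient at one visit, PASI 90 would be scored from the observation while sPGA 0/1 would be scored as failure by rule.

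Both are secondary endpoints at Week 52, and maintenance of response at Week 52 is a stated objective. The Part B summary of sPGA response among those already responding at entry to Part B (SAP Section 10.3.1) would be affected in the same way.

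**Working it through.** **Inputs.** Part B doses are at Weeks 16, 28 and 40 (protocol Table 4.1.4: 1). The visit window is ±7 days at Weeks 28, 40 and 52 (Flow Chart). Intervals and caps are from SAP Tables 6 and 7. Arm sizes are from SAP Section 4.3.

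**1. Reproduce the printed windows.** Part B Day = (week − 16) × 7 + 1, which gives Week 28 = 85, Week 40 = 169, Week 46 = 211, Week 52 = 253 and Week 56 = 281.
- Table 7, Week 52: the split is (169 + 253)/2 = 211, so the window opens on Day 212, as printed. The upper end by the half-interval is 253 + 42 = 295, against 294 printed; the one-day difference has no bearing here.
- Table 6, Week 52: the splits are (211 + 253)/2 = 232 and (253 + 281)/2 = 267, giving [233, 267], as printed.

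**2. Apply the cap.** Upper bound = min(294, last-dose day + 105).

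| Last dose | Part B day | Cap | Table 7 Week 52 window | Table 6 Week 52 PASI window |
|---|---|---|---|---|
| Week 4 (risankizumab arms) | 29 − 112 = −83 | 22 | empty | [233, 267] |
| Week 16 | 1 | 106 | empty | [233, 267] |
| Week 28 | 85 | 190 | empty | [233, 267] |
| Week 28, 7 days late | 92 | 197 | empty | [233, 267] |
| Week 40, 7 days early | 162 | 267 | [212, 267] | [233, 267] |
| Week 40 | 169 | 274 | [212, 274] | [233, 267] |

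**3. Check by visit spacing.** From a Week 40 dose to the Week 52 visit is 253 − 169 = 84 days, and at most 84 + 14 = 98 with both visit windows stretched. That is under 105, so fully dosed patients on schedule keep their data. From a Week 28 dose it is 253 − 85 = 168 days, and at least 168 − 14 = 154. That is over 105, so the Week 52 visit is always lost.

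**4. What happens to the dropped value (SAP Section 10.1.4).**
- Binary endpoints: NRI is primary and scores a missing visit as non-response unless the patient responds both before and after. The Flow Chart schedules no sPGA or joint count after Week 52, so the exception cannot apply.
- Continuous endpoints: LOCF is primary, so an earlier value replaces the observed one.
- The cap sits on one row only. After a last dose at Week 16, the Week 40 sPGA (169 − 1 = 168 days later) is kept, while the Week 52 sPGA is not.

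**5. Size.** The documents do not say how many patients stop drug, stay and attend Week 52. Each such responder costs 1/56 = 1.8 points of the Week 52 sPGA 0/1 rate in a risankizumab arm. The placebo group splits 1:1, so 56/2 = 28, and each costs 1/28 = 3.6 points there. If, as an assumption, there were 1 to 6 per arm, the loss would be 1.8 to 10.7 points (n = 56) or 3.6 to 21.4 points (n = 28). ACR 20 is analysed in the psoriatic arthritis subset, whose size is not given, so each lost responder would weigh more there.

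**6. Could such patients still be responding?** Protocol Section 1.2 reports that 24 weeks after a single administration 71% still had PASI 75 and 48% had PASI 90. Week 28 to Week 52 is also 24 weeks. That was a small phase I trial measured by PASI, so it shows plausibility and gives no rate for this trial.

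**The case against.** The strongest reply is that this is a drafting slip with little reach. Everywhere else the 105-day limit is a safety rule, and a programmer who reads Section 6.0 as a whole might apply it only to laboratory tests and ECG. The Week 52 endpoints are summarised descriptively (SAP Section 10.3). The only tests under multiplicity control are PASI 90 at Week 16. All of this stands and limits the severity. It does not remove the point, because footnote a as written gives a different result from the one the surrounding text implies.

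Three stronger readings go further than the documents allow.

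- *Every patient last dosed at Week 28 or earlier loses Week 52 data.* Patients who leave the trial have the end-of-treatment procedures and a final visit at which no sPGA is scheduled, so the footnote takes nothing from them. Patients with intolerable worsening are taken out of the trial. Those discontinued for an adverse event of worsening disease are non-responders at all later visits under NRI, for PASI and sPGA alike. Placebo patients who do not enter Part B are outside the Part B analyses.
- *sPGA is biased downward in every analysis.* This follows under NRI. Under LOCF, the secondary approach for binary endpoints, an earlier response would be carried forward.
- *The bias is a known 2.5 to 7.5 points.* That range needs 5% to 15% of patients to stop drug and stay, with half of them responding. Neither figure is in the documents.

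**Conclusion.** The point holds on the text as written, for a limited group: patients who stop drug before the Week 40 dose, for reasons other than worsening disease, and still attend Week 52. For them the Table 7 Week 52 window is empty. Observed sPGA and ACR 20 results turn into non-response under NRI, continuous outcomes are replaced by LOCF, and PASI from the same visit is retained.

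The certain size is per patient: about 1.8 points of the Week 52 sPGA rate for each lost responder among 56, or 3.6 among 28. The total depends on a count that the documents do not give.

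A reader might infer that the sponsor chose an on-treatment analysis for Week 52. The wording in Table 2, the absence of the limit in Table 5 and the safety heading on the last-observation rule argue against that. The primary Week 16 comparison, its alpha and its power are untouched. So are the Week 28 endpoints, because that row carries no cap. The rule should be corrected, but it does not threaten the trial's main conclusion.

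**What to change.** Reword Table 7 footnote a so that the upper limit is *the minimum of the upper bound and, for safety analyses, last dose + 105 days*, in line with Table 2. Every ITT efficacy variable then uses the fixed window [212, 294] at Week 52, whatever the date of the last dose, and is treated like PASI.

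The restriction should be by type of analysis and not by variable. Unlike Table 5, Table 7 does not list CRP as an ACR 20 component, so in Part B it is covered only as a laboratory test. Keeping the cap on all laboratory tests would still remove Week 52 CRP, one of the five supporting ACR 20 criteria (protocol Appendix 10.3.3), for the same patients.

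If an on-treatment rule was intended, the SAP should state it and apply it to PASI as well.

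The cost is one phrase in the SAP and one condition in the window derivation, made before the final database lock. No new data, visits or sample size change are needed.
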